9.4 Statistical Analyses

A SAP will be written to provide details of the analysis, along with specifications for tables, listings and figures to be produced. SAPs will be prepared for analyses at the end of 24 weeks of double-blind treatment for objectives and endpoints of this protocol and additional objectives and endpoints specific to the endpoints in the 0367-CL-1201 [MAYO] Protocol. Other SAPs will be prepared for analysis at the end of 76 weeks of treatment for objectives and endpoints of this protocol and additional objectives and endpoints of this protocol and additional objectives and endpoints of this protocol and additional objectives and endpoints specific to the 0367-CL-1201 [MAYO] Protocol. The SAPs for the 24-week double-blind treatment analysis and 76-week treatment analysis will be finalized before unblinding for 24-week data and before database lock for 76-week data, respectively. Changes from the planned analyses in the final SAP that impact the statistical analyses will be justified in the CSR. Additionally, the interim analysis plans will be finalized prior to the interim analyses.

9.4.1 General Considerations

In general, continuous data will be summarized with descriptive statistics (number of participants, mean, SD, minimum, median and maximum), frequency and percentage for categorical data. Percentage by categories will be based on the number of participants with no missing data (i.e., will add up to 100%).

Baseline will be defined as the last non-missing observation prior to first administration of IP, unless otherwise specified.

Demographics and baseline characteristics (age, sex, race and ethnicity, body weight, height and BMI) and genetic abnormality for PMM will be summarized by treatment group and overall for the Safety Analysis Set (SAF).

The number and percentage of participants who complete and discontinue 24 weeks of treatment and reasons for treatment discontinuation will be presented for all randomized participants by treatment group and overall. All disposition details and dates of first and last evaluations for each participant will be listed.

All previous and concomitant treatment and medical history will be listed. Medical history will be coded using MedDRA and will be summarized by system organ class (SOC) and preferred term (PT) by treatment group and overall for the SAF. All IP exposure data will be listed.

9.4.2 Analysis of Efficacy

Efficacy analysis will be conducted on the Full Analysis Set and statistical testing will be performed to compare each dose group of ASP0367 and placebo group at the 2-sided 0.10 significance level. Details will be provided in the SAP.

9.4.2.1 Analysis of Primary Endpoint

For primary efficacy endpoint, change from baseline in distance walked on the 6MWT at week 24, a mixed model for repeated measures (MMRM) with treatment groups (3 level: ASP0367 75 mg, ASP0367 30 mg, and placebo group), week (weeks 4, 12 and 24) and site group (2 level: Mayo clinic_Minnesota; Non-Mayo clinic_Minnesota) as factors, with baseline measurement as a covariate, as well as an interaction of treatment by week and an interaction of baseline measurement by week. If the number of participants from either site group is small, the site group will be removed from the model. It will be determined before the unblinding and pre-defined in the SAP.

The 6MWT evaluated below will be included in the analysis.

• For participants who consented for this study in Protocol Version 7.0 or former version and did not re-consent to Protocol Version 8.0 or later by week 24: the 6MWT evaluated until 7 days after the last dose of IP for the double-blind treatment period of the study or moving to the OLE or day 182, whichever comes first.

• For participants who consented or re-consented this study in Protocol Version 8.0 or later version by week 24: the 6MWT evaluated until 7 days after the last dose of IP for the double-blind treatment period of the study.

9.4.2.2 Sensitivity Analysis/Supplementary Analysis

Sensitivity analysis and supplementary analysis will be performed for the primary endpoint using the MMRM based on the Full Analysis Set to assess the robustness of the primary efficacy results. The following analyses are planned:

- MMRM with additional covariate(s).
- MMRM including the data after treatment discontinuation.

9.4.2.3 Analysis of Secondary Endpoints

The change from baseline to week 24 in 5XSTS and MFIS will be analyzed using the same MMRM as with the primary endpoint.

For Neuro-QoL Short Form Fatigue and Lower Extremity Function (Mobility) scores, a transformed T-score will be used, which rescale raw scores into standardized scores with a mean of 50 and a standard deviation of 10. Change of T-scores from baseline to week 24 will be analyzed using the same MMRM as with the primary endpoint.

For PGIC score at week 24, generalized estimating equation model will be used with treatment group (3 level: ASP0367 75 mg, ASP0367 30 mg, and placebo group), week (weeks 4, 12 and 24) and site group (2 level: Mayo clinic_Minnesota; Non-Mayo clinic_Minnesota) as factors, as well as an interaction of treatment by week. In addition, responder analysis will be used. Participants with scores of 1 (Very Much Improved), 2 (Much Improved) and 3 (Minimally Improved) will be considered as responders, whereas participants with scores of 4 (No Change), 5 (Minimally Worse), 6 (Much Worse) and 7 (Very Much Worse) will be treated as nonresponders.

For PGIS score, change from baseline to week 24 will be analyzed using generalized estimating equation model with treatment group (3 level: ASP0367 75 mg, ASP0367 30 mg, and placebo group), week (weeks 4, 12 and 24) and site group (2 level: Mayo clinic_Minnesota; Non-Mayo clinic_Minnesota) as factors, baseline value as a covariate, as well as an interaction of treatment by week and an interaction of baseline value by week.

For the secondary endpoints, the multiplicity of statistical comparison will not be adjusted.

9.4.2.4 Analysis of Exploratory Endpoints

For 6MWT, 5XSTS, Neuro-QoL Short Form Fatigue and Lower Extremity Function (Mobility) scores, change from baseline to week 4 and 12 will be summarized by treatment group and time point. The change from baseline in minute-by-minute analyses (i.e., 6th vs 1st) of 6MWT at weeks 4, 12 and 24 will be summarized by treatment group.

For MFIS score and PGIS scores, change from baseline to weeks 4 and 12 will be summarized by treatment group and time point. Moreover, PGIC scores at weeks 4 and 12 will also be displayed in the same way.

For the EQ-5D-5L descriptive systems, the number and percentage of participants will be summarized by scored level (1 to 5) of each dimension and treatment group, as well as time point. Change from baseline in EQ-VAS and EQ-5D-5L index values at weeks 4, 12 and 24 will be summarized by treatment group and time point.

9.4.3 Analysis of Safety

Safety analyses will be conducted on the SAF. Summary tables and listings of safety information will be provided in the SAPs.

9.4.3.1 Adverse Events

AEs will be coded using MedDRA.

A TEAE is defined as below:

- For participants who consented for this study in Protocol Version 7.0 or former version and did not re-consent to Protocol Version 8.0 or later version by week 24: an AE observed after starting administration of the IP to 28 days after the last dose of IP for the double-blind treatment period of the study or moving to the OLE or day 182, whichever comes first.
- For participants who consented or re-consented to this study in Protocol Version 8.0 or later version by week 24: an AE observed after starting administration of the IP to 28 days after the last dose of IP for the double-blind treatment period of the study or moving to the OLE, whichever comes first.

The number and percentage of participants with TEAEs, SAEs, AEs leading to withdrawal of treatment and AEs related to IP will be summarized by SOC, PT and treatment group. The number and percentage of AEs by severity will also be summarized. The worst severity will be summarized if the same AE is recorded more than once for a participant.

An IP-related TEAE is defined as any TEAE with a causal relationship of "yes" by the investigator.

AE data will be listed.

9.4.3.2 Laboratory Assessments

For quantitative clinical laboratory measurements (hematology, biochemistry and urinalysis), descriptive statistics will be used to summarize results and change from baseline by treatment group and time point.

Laboratory data will be listed.

9.4.3.3 Vital Signs

Descriptive statistics will be used to summarize vital sign results and changes from baseline by treatment group and time point.

Vital signs data will be listed.

9.4.3.4 Body Weight

Body weight data will be displayed in listings.

9.4.3.5 Electrocardiogram

9.4.3.5.1 Routine 12-lead Electrocardiogram

The routine 12-lead ECG results will be summarized by treatment group and time point.

All ECG interpretations will be displayed in listings.

9.4.3.5.2 Continuous 12-lead Electrocardiogram

For all analyses, replicates at each time point will be averaged for each continuous 12-lead ECG parameter.

Descriptive statistics will be used to summarize the continuous 12-lead ECG parameter results and changes from baseline by treatment group and time point.

The number and percentage of participants with absolute QTcF interval \leq 450 msec, > 450 msec, > 480 msec, > 500 msec will be provided by treatment group at each time point and overall by visit. Similar summary information will be provided for QTcF interval increases from baseline of \leq 30 msec, > 30 msec and > 60 msec.

Continuous 12-lead ECG data (individual replicates and the averages) will be listed.

9.4.3.6 Echocardiogram

Echocardiogram results will be displayed in listings.

9.4.3.7 Columbia-Suicide Severity Rating Scale

C-SSRS data will be summarized by treatment group and time point.

9.4.4 Analysis of Pharmacokinetics

Descriptive statistics will include n, mean, SD, minimum, median, maximum, coefficient of variation (CV), geometric mean and geometric CV, where applicable. Noncompartmental analysis will be performed on the dense pharmacokinetic samples from participants who have already provided these and will be reported in the CSR. Further details on the calculation of the pharmacokinetic parameters will be provided in the SAPs. No noncompartmental analysis will be conducted on samples from new participants. Only C_{trough} will be reported for new participants in the CSR, and pharmacokinetic profiles will be analyzed via population pharmacokinetics.

9.4.5 Analysis of Pharmacodynamics

Analysis of pharmacodynamics data for participants enrolled prior to implementation of Protocol Version 9.0 (Substantial Amendment 8) will differ from analysis of data for participants enrolled starting with Protocol Version 9.0 (Substantial Amendment 8).

9.4.5.1 Analysis of Treatment-emergent Gene Expression

Summaries of absolute values and relative changes from baseline for each gene by scheduled sample time point and treatment group will be provided. Baseline for gene expression is predose measurements on day 1. Absolute values and relative changes from baseline for gene expression will be listed. If deemed appropriate, gene expression data may be log-transformed and/or graphically summarized.

9.4.5.2 Estimation of Pharmacodynamic Parameters

Further details on the calculation of the pharmacodynamic parameters will be provided in the SAP.

9.4.6 Other Analyses

9.4.6.1 Analysis of Biomarkers

Descriptive statistics (e.g., n, mean, SD, median, minimum CV, geometric mean and geometric CV where applicable) will be used to summarize the effects of ASP0367 (result and relative change from baseline) for serum FLNC, CYC and ALDOA, and urinary TITIN. The summaries will be presented by treatment group and by scheduled sampling time point.

For 24-week treatment analysis, a summary will be provided by treatment group.

Descriptive statistics will be used to summarize results and relative change of biomarker measurements from baseline by time point.

All biomarker data (results and relative change from baseline) will be listed. In addition, biomarker data may be summarized graphically and/or descriptively as they relate to clinical measures, as applicable. Additional exploratory biomarker analyses may be performed and defined in a biomarker SAP.

9.4.6.2 Analysis of Genotyping

Polymorphisms of genes PPAR δ and PPARGC1A will be tabulated. In addition, polymorphisms of genes may be summarized graphically and/or descriptively as they relate to clinical measures, as applicable. All analyses described in this section are based on availability of the data.

9.4.6.3 Exposure-response Analysis

The relationship between PK parameters (e.g., C_{trough}) of ASP0367 and efficacy, safety and pharmacodynamics will be investigated. The details of this analysis will be described in the SAP. Other exposure metrics such as $C_{ave,ss}$ may be investigated using pharmacokinetic parameters estimated in population pharmacokinetic analysis and reported separately from the CSR, as calculable pending the population PK model.

9.5 Additional Conventions

If the start and stop dates of AEs and concomitant medications are incomplete, imputed dates will be used to determine whether an AE is/is not treatment emergent or to allocate a concomitant medication to the study period it was taken.

Refer to the SAPs for details of the definition for analysis windows to be used for analyses by visit.

9.6 Interim Analysis

9.6.1 Interim Analysis of Efficacy

The analysis of futility and of efficacy will be performed when approximately 30 participants complete the 6MWT assessment at week 24 for the evaluation of whether a change may be observed in the primary endpoint. If no appreciable change is noted, the study may be stopped due to futility. If efficacy is observed, the study may continue or may be brought to a completion in order to proceed to a final full analysis of the study.

The change from baseline in distance walked on the 6MWT at week 24 will be analyzed using the same MMRM as with the primary endpoint excluding the site group from the model to decide whether the study will continue.

Analysis of Futility

For the futility stop, the study may be stopped if the conditional probability of achieving the criteria below at the final analysis is less than 10%.

Criteria: Lower limit of the 90% CI for the difference is greater than 0 m AND the point estimate of the difference between the ASP0367 75 mg group and the placebo group is greater than 30 m.

In addition to 6MWT at week 24, outputs for participant disposition, demographics and the secondary endpoints 5XSTS, Neuro-QoL Short Form Fatigue score, Neuro-QoL Short Form Lower Extremity Function (Mobility) score, MFIS, PGIC, and PGIS at week 24 may be analyzed at the interim analysis.

The interim analysis outputs will be prepared by an external statistician and presented to the DMC for interim analysis who will make recommendations about the ongoing conduct of the study.

Details of the analysis will be defined in the interim analysis plan.

Analysis of Efficacy

For the efficacy stop, a two-stage group sequential design with Lan-DeMets alpha-spending function determined by means of the O'Brien-Fleming approach will be used to preserve the overall two-sided type I error rate of 0.10 between this single interim analysis and the final analysis. If the p-value of the comparison between ASP0367 75 mg and placebo groups at interim analysis is lower than the boundary determined by O'Brien-Fleming approach, efficacy would be considered to be achieved at week 24.

9.6.2 Interim Analysis of Pharmacokinetics and Pharmacodynamics

An interim analysis of pharmacokinetic and pharmacodynamic data may be conducted with data from approximately 30 participants. These analysis results will help in understanding the results of the interim analysis for futility and efficacy. The interim analysis will be detailed in

a separate interim pharmacokinetic and pharmacodynamic analysis plan. Personnel external to the study team will be specified in the interim analysis plan and will analyze the pharmacokinetic and pharmacodynamic data and prepare a report to be shared with the DMC and others. Only mean values and figures with variability will be shared with the study team and DMC to maintain the study team blind before database lock.

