4 STUDY DESIGN AND DOSE RATIONALE

4.1 Overall Study Design

This is a randomized, double-blind, placebo-controlled, oral dose, phase 2 study to evaluate the dose response of ASP0367 on functional improvement relative to placebo, safety and tolerability in participants with PMM. Efficacy (i.e., functional improvement) will be assessed by a functional motor test, 6MWT. The study consists of the following portions: screening (4 weeks); double-blind treatment period with 2 doses of ASP0367 vs matching placebo (24 weeks); and follow-up (4 weeks).

A 24-week treatment analysis of efficacy and safety will be the primary focus. Since participants enrolled in the study prior to implementation of Protocol Version 9.0 (Substantial Amendment 8), which removes the 52-week OLE period, may have a treatment duration of up to 76 weeks, a separate treatment analysis will also be conducted at later timepoints up to 76 weeks as per available data [Section 9]. An unblinded, independent Data and Safety

Monitoring Board (DSMB) will assess the overall safety and tolerability of ASP0367 throughout the course of the study as summarized in [Section 10.1.5.1.1].

Approximately 66 participants will be enrolled. At randomization, participants will be randomly placed into 1 of 3 arms (30 mg ASP0367, 75 mg ASP0367 or placebo; n = 22 for each arm) at a ratio of 1:1:1. Stratified randomization by site group (2 level: Mayo clinic_Minnesota; Non-Mayo clinic_Minnesota) will be applied.

At week 24 while enrollment continues, data from the first approximately 30 evaluable participants will be reviewed in an interim analysis, as described in [Section 9.6], to determine if the futility or efficacy stopping criteria are met while the study is ongoing. An Astellas internal DMC for interim analysis will assess the futility and efficacy of the study treatments and make recommendations about the ongoing conduct of the study as summarized in [Section 10.1.5.1.2]. An interim analysis of pharmacokinetic and pharmacodynamic data will also be reviewed by the DMC.

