6.3 Randomization and Blinding

6.3.1 Blinding Method

This is a double-blinded study. Participants will be randomized to receive ASP0367 or placebo in a blinded manner such that neither the investigator, sponsor's study management team, clinical personnel, caregiver, nor the participant will know which IP is being administered in the double-blind treatment period of the study. The randomization number will be assigned based on information obtained from the Interactive Response Technology (IRT) system.

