6.3.3 Retention of the Assignment Schedule and Procedures for Treatment Code Breaking

The randomization list and treatment assignment blind will be maintained by the IRT system.

The independent DSMB will be provided with access to the treatment assignment for periodic review of the overall safety and tolerability data. Its operation will be documented in the DSMB Charter.

The DMC will be provided with access to the treatment assignment for review of the interim analysis data. Its operation will be documented in the DMC Charter.

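### Protocol 9.6.2 lets the study team receive interim PK/PD means before database lock; if these are shown by arm, a team meant to stay blinded would see whether each dose is active

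*Protocol*

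**What the plan says.** Protocol section 9.6.2 opens: "An interim analysis of pharmacokinetic and pharmacodynamic data may be conducted with data from approximately 30 participants". The results are meant to help interpret the futility and efficacy interim. Staff outside the study team do the analysis and "prepare a report to be shared with the DMC and others"; who those others are is not stated. The release rule is: "Only mean values and figures with variability will be shared with the study team and DMC", with the stated aim of keeping the study team blind until the database is locked. Further detail is left to a separate interim PK/PD analysis plan, which is not among the documents.

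Other sections bear on who may see such results:

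- **Section 4.1** sets the timing of the interim: "At week 24 while enrollment continues, data from the first approximately 30 evaluable participants will be reviewed in an interim analysis". It then says that the DMC will also review the PK/PD interim, and it names no other reviewer. The synopsis (1.1) says the same.
- **Section 6.3.1** provides that neither the investigator nor the sponsor's "study management team, clinical personnel, caregiver, nor the participant will know which IP is being administered" during the double-blind period.
- **Section 6.3.3** says: "The DMC will be provided with access to the treatment assignment for review of the interim analysis data".
- **Section 7** (opening list) keeps laboratory results that might reveal treatment from sites and other blinded staff until the study is unblinded.
- **Section 9.4.5.1** describes the planned gene-expression output: "Summaries of absolute values and relative changes from baseline for each gene by scheduled sample time point and treatment group will be provided".
- **Section 9.6.1** has the efficacy outputs prepared by an external statistician and presented to the DMC. The study team is not mentioned.

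**The concern.** The release rule in 9.6.2 aims to keep the study team blind, yet it names that team as a recipient of interim results before lock. Summarising the data prevents anyone from reading off an individual's assignment. It does not prevent the reader from seeing how the arms differ.

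The sensitive part is the pharmacodynamic data. Section 2.2.3.2 reports treatment- and dose-dependent up-regulation of PPARδ target genes in healthy volunteers, and an exploratory objective in section 3 links functional improvement to gene-expression markers. A by-arm display would tell the team whether each dose is pharmacologically active in patients with the disease, partway through a trial that is still collecting its primary outcome.

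Two things could then be influenced. The first is conduct: the 6MWT depends on effort, and Neuro-QoL, MFIS, PGIC and PGIS are self-reported. The second is analysis. Some choices stay open until unblinding: whether to keep site group in the model (9.4.2.1), which extra covariates to use in the sensitivity analysis (9.4.2.2), and the final SAP (9.4).

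**Working it through.** **1. Recipients, side by side**

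| Protocol section | Material | Named recipients |
|---|---|---|
| 1.1, 4.1 | PK/PD interim | DMC |
| 9.6.1 | Efficacy interim outputs | DMC |
| 9.6.2 | PK/PD report | DMC and unnamed others |
| 9.6.2 | PK/PD means and variability figures | Study team and DMC |
| 7 | Laboratory results that might unblind | Not blinded staff, until unblinding |

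The wider release appears only in 9.6.2.

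**2. Are the means by arm?** Section 9.6.2 does not say. Two parts of the protocol point that way. The gene-expression summaries in 9.4.5.1 are by treatment group. The purpose given in 9.6.2 is to help understand the futility and efficacy result, which in 9.6.1 is a comparison of 75 mg with placebo. Means pooled over three arms would do little to explain such a comparison. By-arm display is therefore the natural reading, but it is an inference.

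**3. What would be disclosed?** With 1:1:1 allocation, about 30 / 3 = 10 participants per arm contribute. Ten-person means with variability do not identify anyone's assignment. They do show the placebo, 30 mg and 75 mg averages next to each other. Blinding to individual codes survives; blinding to interim group differences does not.

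**4. How much of the trial could follow the release?**

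- Inputs from section 9.2: 60 participants required once the interim is allowed for, about 10% dropout, 66 randomized.
- Check of the plan's figure: 60 × 1.10 = 66. Dividing instead, 60 / 0.90 = 66.7, rounded up to 67. The one-participant difference has no bearing here.
- Input from 4.1 and 9.6.1: about 30 evaluable participants with a week-24 6MWT at the interim.
- Like for like, evaluable against evaluable: 60 − 30 = 30, and 30 / 60 = 50%.

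The SAP (6.7.1) reports that the interim used the first 33 participants who had completed week 24 or discontinued. That count includes dropouts, so it belongs with the 66: 66 − 33 = 33, or 50%. Applying the plan's ratio, 33 × 60 / 66 = 30 would be evaluable, which agrees.

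The 50% is an upper bound. Participants who reach week 24 between the data cut and the release are counted as exposed although they would not be, and the figure assumes that enrolment runs to 66. The documents give no basis for calculating the size of any bias.

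**The case against.** The case on the other side is substantial.

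- **The text is narrower than it first looks.** A reader might infer that the full interim report goes to the study team. It does not: the team gets means and figures, and the report goes to the DMC and unnamed others. The analysis is also optional in 9.6.2, although 4.1 speaks of it as planned. Both points stand.
- **By-arm display is not stated.** The missing PK/PD plan might specify pooled or masked displays. This stands as a limit. It is also a reason to put the restriction in the protocol.
- **Section 6.3.1 concerns which product a person receives.** Read strictly, group means do not breach it, and section 7 already bars results that might unblind. A reader might infer a flat contradiction; it is fairer to say that 9.6.2 fits poorly with both sections and needs to be reconciled with them.
- **The route to bias is largely undocumented.** The study team is not defined, its duties are not set out, and nothing sends these results to investigators, 6MWT assessors or participants. The 6MWT is video recorded where site policy allows, eligibility waivers are barred, and the main model terms, test order and alpha are fixed. These points limit the likely effect. They do not explain why the team needs the data.
- **DMC access.** A reader might see a conflict between 6.3.3, which gives the DMC assignments, and 9.6.2, which gives it summaries. The two are compatible: a committee can hold codes and still receive summary displays.
- **Practical reach.** The SAP says that no participants were evaluated under protocol version 8.0 or later and that the internal committee recommended stopping for futility.

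**Conclusion.** The point holds as a weakness in the plan. Section 9.6.2 permits release of interim PK/PD means to a team that is meant to stay blind, before lock and, on the timing in 4.1, while enrolment continues. If the means are by arm, as 9.4.5.1 and the stated purpose imply, the team would learn whether each dose separates from placebo on target-gene response.

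At most about 30 of 60 evaluable participants (50%) could have their week-24 6MWT after release. This rests on full enrolment, the planned interim size and immediate release. A reader might set the 30 evaluable participants against the 66 randomized and arrive at 36 of 66 (55%). That mixes two populations, because the 66 include the roughly 10% expected to drop out.

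A reader might also infer that the trial was in fact compromised. The documents do not support that: they do not say whether the PK/PD interim was done or whether its results were shared.

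**What to change.** In section 9.6.2:

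1. Restrict any by-arm interim PK/PD results to the DMC and the external analysts who prepare them, until the database lock that triggers unblinding.
2. Delete the study team as a recipient, or limit it to results pooled across arms that cannot reveal a difference between groups.
3. Delete the reference to other recipients of the report, or name them by role.

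Carry the same recipient list into the interim PK/PD analysis plan. This brings 9.6.2 into line with 4.1, 6.3.1, section 7 and 9.6.1. The cost is protocol and plan wording, and the study team waits until lock for group-level PK/PD results. The DMC loses nothing it needs to interpret the futility and efficacy result.
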